2. In more severe cases, if a block increases active range of motion or allows for much greater passive range of motion, it implies the muscle has not contracted but the spastic drive it is too overactive for the toxin and therapy to overcome its pull. Thus, there is the consideration for a cryoneurotomy, radiofrequency or surgical neurectomy, will be explored. Each of which will have specific indications. Cryoneurotomy, is a percutaneous procedure targeting easily identified large motor branches that do not have a sensory component to avoid loss of sensation. Thus, only large motor nerve branches to specific muscles that can be identified are the target for this procedure. This includes, the branches of the musculocutaneous nerve to the brachialis and biceps, the radial nerve to the brachioradialis, the pectoral nerve to the pectoral muscles. A median nerve to the hand is possible if the patients reports no loss of sensation to successive blocks in a paralysis clenched fist. Surgical micro fascicular neurectomy allows of

exquisite intra-operative dissection of most muscles of the upper extremity, including the muscles controlling wrist and finger function, shoulder and elbow. More individual muscles can be targeted with this option.

3. In patients where no change is found, muscle and joint contracture are present which require more extensive surgery to either cut tendon (tenotomy), muscle lengthening, or capsular release of a joint.
4. Patients undergo the less invasive procedure of neurotomy or choose to next undergo a surgical procedure based on their outcomes as part of our clinics standard of care.

Power Over:

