4- Patients satisfaction in achieving their goals after the procedure as assessed by Goal Attainment Scale³⁸. Based on this scale participants will be asked for 3 main goals that they desire to achieve after the intervention. The baseline score will be (-1) and they will be interviewed again at 1, 3, 6, 9 and 12 months, to record how they reported their achievement. The scores of (-2), (-0.5), (0), (1) and (2) will be assigned if they feel that their condition is worse than before, better but not as good as expected, as expected, better than expected and much better than expected. All goals will be weighted equally, and final score will be calculated based on the available formula, in each session. The higher score is presenting of better outcome.

Secondary Objective:

1- Upper limb function changes as assessed by Box and Block test. Participants will be in sitting position and will be asked to move the cubes from one part to the other part in 1 minute. The test will be done in baseline and in 1, 3, 6, 9 and 12 months.

2- Changes in pain as assessed by Brief Pain Inventory Questionnaire. This is a self-administered questionnaire that will be provided for participants for filling out at baseline and in 1, 3, 6, 9 and 12 months after the intervention. The Patient will ask to answer each question by choosing a number between 0 to 10, and the final score is calculating by adding these numbers together and then divided by 4. The result will show the severity of patient pain out of 10. (0 means no pain and 10 means the worst pain that can be imagine)

3- Changes in the Hand resting position as assessed by Keenan Scale (1987)³⁶. Participants will be assessed by an independent examiner and based on available scale their hand position will be graded. Grade 1 is the minimum deformity while grade 5 is the maximum deformity which is presented by clenched fist and palmar hygiene problem. The assessment will be done at baseline and in 1, 3, 6, 9 and 12 months.

4- Changes in thumb deformity (position of thumb in relation to other fingers) as assessed by House Scale (1981)³⁵. Participants will be assessed by an independent examiner and based on available scale their thumb position will be graded between 1 to 4. Grade 1 is the minimum deformity and 4 is the maximum deformity. The assessment will be done at baseline and in 1, 3, 6, 9 and 12 months.

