5- Changes in hand function as assessed by House Functional Scale (1981)³⁵. The test will be done by an independent examiner and participants will be asked to pick a cube on the table while they are in a sitting position. Based on the available scale (0= No movement and 8= spontaneous use, complete) their hand function will be graded in baseline, 1,3,6,9 and 12 months after intervention.

6-Changes in hand grip strength as assessed by dynamometer and will be recorded in KG in baseline and 1,3,6,9 and 12 months. The test will be done by Jamar Dynamometer and will be recorded as KG.

Hypothesis:

Surgical or percutaneous ablative procedures can improve range of motion, function and patient satisfaction in patients that have plateaued or are refractory to botulinum focused therapies after screening patients with an ultrasound (US)-guided electrical (e)-stimulation DNB with 2% lidocaine to determine the most responsible muscle(s) in the spastic upper extremity.

Study Design:

This cohort study has a prospective intensive repeated measures study design. Repeated measures design is a research design that involves multiple measures of the same variable taken on the same subjects either under different conditions or over two or more time periods. Intensive denotes more measurements over time. Patients diagnosed with spasticity vary widely in function and limb usage; thus, the benefit of using this design is that it allows participants to serve as their own control.

Design Details:

Patients with upper extremity spasticity will be recruited from the multidisciplinary spasticity clinic. All study patients will have been assessed in the interdisciplinary team consisting of a physiatrist, hand surgeon, and an interventional anesthesiologist. US-guided e-stimulation DNB with 2% lidocaine will be used as a screening tool to determine the most responsible muscle(s) for the spastic upper extremity. Pre- and post-block maximum active and passive range of motion in the spastic muscle group., and the presence of fixed joint contractures will be assessed.

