Based on the results of the DNB, patients and their clinician selection the mutually selected most appropriate treatment streams: altered toxin dosage, surgical micro fascicular neurectomy, percutaneous cryoneurotomy, radiofrequency neurotomy, surgical tenotomy, or unlikely to benefit from further procedures. The choice of which stream is based on the response of the nerve block. All patients with contracture will need a tendon or muscle surgery to improve range of motion. Patients with increased range of motion in isolated regions, such as the shoulder adductors, elbow flexors, can undergo cryoneurotomy on their isolated motor nerve. Patients with increased range of motion in the finger and wrist flexors require nerve surgery as well as possible muscle and tendon surgery to the motor fibres cannot isolated for nerve ablation in the region. The decision to not offer a procedure and increase toxin is reserved for the milder cases where range of motion is quite good, but the nerve block reveals even more loosening. This group will not be part of our study as that is the typical course of treatment.

Beginning of Study:

After surgical or percutaneous neuroablative procedures are selected patients will be invited to enroll in the study.

There will be no change in usual care after the procedures. Units of BoNT used will be tracked. All patients will be assessed at each stage by a single assessor to administer measurements and test scores. This study is not blinded. Blinding is not typical in surgical studies. It is too difficult to hide scars. The skin will need to be exposed to ensure proper measurements. The assessor would also intuitively guess by the deformity of the arms which procedures were most likely undertaken.

Initial Contact Letter:

Once a patient elects to undergo a nerve or surgical procedure they will receive a study information package at the time of decision. All patients have routine follow ups in clinic and the assessment will be done in the same days of their visits. All patients will be offered to take the package home to consider or fill out in clinic. Patients will receive one reminder phone call or email at their preference to determine if they will participate. All patients will be given a reminder call by our research assistant two weeks after unless they opt out.

Surgical Neurectomy Stream.

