The protocol follows the same assessment and preparation as cryoneurotomy. [name] has performed thousands of these interventions to nerves. They are also percutaneous nerve procedures. The protocol is quite similar as cryoneurotomy, with the exception of the probe. Pulsed radiofrequency (PRF), a technique introduced in the 1990's³³, is known to be safe and effective on nerve structures and particularly relieving pain. It delivers an electrical field and heat bursts to targeted nerves or tissues without damaging these structures. Previous studies have used continuous radiofrequency (CRF)³⁴ exposes target nerves or tissues to a continuous electrical stimulation and ablates the structures by increasing the temperature around the RF needle-tip. PRF does not produce sufficient heat to cause structural damage. The availability of cryoneurotomy is quite limited to the lack of machines in Canada, where as radiofrequency is widely performed in hospitals and clinics all across Canada. To date our availability of time on the cryoneurotomy equipment is limited, and pulsed radiofrequency will allow for shorter waits.

Sample Size Justification. Statistical Analysis

Sample Size: N = 50

This is a pilot study. A convenience sample of 50 patients is anticipated, based on the volume of patients that has been triaged in this clinic to date. Over 100 patients have been triaged in 18 months, so it is anticipated that 50 target patients to be fully completed treatment in 18 months. At 4-6 (divided between surgical and interventional) patients per month for 12 months, this is achievable based on this clinical experience. Analysis will be individualized per patient, as each will undergo a unique procedure. Statistical analysis will address each patient stream individually. The outcome measures that will used are standard clinical and functional measures, but effect sizes are not readily available from previous studies in order to formally calculate sample size. Furthermore, this study uses an exploratory prospective cohort design, rather than a parallel group trial design, limiting the rationale for providing a sample size calculation.

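### Hand posture, thumb posture and grip are analysed by stream without regard to treated region, so each stream's result depends on its mix of treatment sites

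*Combined protocol and SAP*

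**What the plan says.** **Who is measured.** The Inclusion Criteria admit adults with functionally impairing spasticity anywhere in the upper extremity; hand involvement is not required. Secondary Objective item 3 is "Changes in the Hand resting position as assessed by Keenan Scale", and it adds: "Participants will be assessed by an independent examiner and based on available scale their hand position will be graded". Item 4 is "Changes in thumb deformity (position of thumb in relation to other fingers) as assessed by House Scale", with the same open population: "Participants will be assessed by an independent examiner and based on available scale their thumb position will be graded between 1 to 4". Item 6 is "Changes in hand grip strength as assessed by dynamometer". All three are taken at baseline and at 1, 3, 6, 9 and 12 months, and Beginning of Study has every patient assessed at each stage.

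**Where the procedures act.** Item 2 of the triage pathway (under Need for multidisciplinary interventions) gives the cryoneurotomy targets as "the branches of the musculocutaneous nerve to the brachialis and biceps, the radial nerve to the brachioradialis, the pectoral nerve to the pectoral muscles". It then allows a median nerve procedure for the hand, on the condition that repeated blocks cause no sensory loss in a clenched fist. The same item says that surgical neurectomy can reach most upper-limb muscles, from shoulder to fingers. Design Details repeats the percutaneous focus ("Patients with increased range of motion in isolated regions, such as the shoulder adductors, elbow flexors, can undergo cryoneurotomy on their isolated motor nerve") and sends finger and wrist flexors to nerve surgery, because their motor fibres cannot be isolated for ablation. The Pulsed radiofrequency Stream has no target list of its own and refers back to the cryoneurotomy assessment and preparation.

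**How it is analysed.** The statistical section states: "Statistical analysis will address each patient stream individually". It plans paired tests and mixed models of within-person change. Treated muscle or region does not appear as a covariate, a stratum or the basis of an analysis set.

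**The concern.** The Keenan, House thumb and grip measures describe the fingers and thumb. A patient treated only at a pectoral or musculocutaneous branch has had no direct treatment of the muscles that set those scores. The triage rule links stream to body region, and the analysis then summarises hand outcomes by stream without taking region into account.

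Two different problems follow. In a stream that mixes sites, the mean change blends patients whose hand was treated with patients whose hand was not, so it estimates neither group. In a stream where almost nobody is treated at the hand, the mean may be accurate but describes change away from the treated site, and it should not be read as the effect of the procedure on the hand. In both cases a reader of the results table could not tell whether a small change means that the procedure failed or that it was applied elsewhere.

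**Working it through.** **1. The plan's own figure.** The only sample-size figure is N = 50, a convenience sample justified by clinic volume. The stated accrual of 4 to 6 patients per month for 12 months gives 4 × 12 = 48 to 6 × 12 = 72, a range that contains 50. The plan gives no effect size, standard deviation, stream size or site mix, so nothing in it fixes the size of the problem.

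**2. General form.** Let q be the share of a stream treated at a wrist, finger or thumb muscle, d the mean change in those patients, and u the mean change in the rest. Then

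stream mean = q × d + (1 − q) × u.

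It equals d only if q = 1 or u = d. If q = 0 it equals u, which carries no information about d.

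**3. Is u zero?** The documents do not establish it. Item 6 of the Cryoneurotomy Stream expects botulinum toxin to be redistributed after the procedure, and the timeline note under Efficacy Evaluation allows more than one type of procedure per patient. Either could change hand scores in a patient first treated at the shoulder or elbow. If u lies between 0 and d, the stream mean falls short of d by less than the simple formula q × d implies. If u has the opposite sign to d, it falls short by more. If u exceeds d, the stream mean overstates d.

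**4. Illustration with u = 0 (assumed).** For an assumed gain of 2 Keenan grades in treated hands, q × d gives 1.00 × 2 = 2.0, 0.50 × 2 = 1.0, 0.25 × 2 = 0.5 and 0 × 2 = 0.

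**5. Precision, same assumption.** Take d in standard deviation units, a within-group SD of change of 1, and a two-sided paired t-test at 0.05. The SD in the blended stream is √(1 + q(1 − q)d²). With assumed d = 0.8 and n = 25 (50/2, also assumed):

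| q | Mean, q × d | SD | Mean/SD | Power, whole stream | Power, hand-treated only |
|---|---|---|---|---|---|
| 1 | 0.80 | 1.000 | 0.800 | 97% | 97% (n = 25) |
| 0.5 | 0.40 | √1.16 = 1.077 | 0.371 | 43% | 71% (n = 12) |
| 0.25 | 0.20 | √1.12 = 1.058 | 0.189 | 15% | 36% (n = 6) |

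At q = 0.25 and n = 25, whole-stream power runs from 9% (d = 0.5) to 20% (d = 1.0). With n = 12 (about 50/4) and d = 0.8 it is 71%, 22% and 9% at q = 1, 0.5 and 0.25. Restriction by site brings the mean back to d, but the groups are small.

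**6. Which streams are affected.** Surgery is described as reaching wrist and finger muscles as well as elbow and shoulder, so its q can lie well between 0 and 1, where blending is clearest. For cryoneurotomy, and for radiofrequency by reference, the listed targets suggest a low q, so the off-target reading is the more likely one there.

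**The case against.** The strongest reply is that this is a 50-patient exploratory pilot in which each patient serves as their own control. The statistical section says that analysis is individualised per patient, and the mixed models yield individual parameters. The primary measures already follow the site or the patient: Tardieu on the tested joints, and goals chosen by the participant. Only three of six secondary outcomes are at issue, and the diagnostic block already identifies the responsible muscles, so treated site may well be recorded in practice.

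Much of this stands, and it limits the reach of the point. It does not remove it. Individual trajectories give no rule for which patients make up a stream result, and the plan commits to analysis by stream.

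A reader might go further and infer that surgery will look better than the percutaneous procedures merely because of where it is applied. The documents do not support this as a flaw in a planned inference: no between-stream comparison is planned, the design is described as a cohort rather than a parallel-group trial, and surgery is itself mixed-site. Only an informal side-by-side reading of stream results is at risk.

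A reader might also infer floor effects on Box and Block and the House Functional Scale from the background example of a patient who cannot use the hand. That is one illustration, and no baseline distribution is given.

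**Conclusion.** The point holds as a matter of interpretation of three secondary outcomes. As planned, the within-stream mean change in Keenan, House thumb and grip depends on how many patients in the stream were treated at the hand, and the plan provides no means of separating them. This applies to every stream with mixed sites, surgery included; a stream with few or no hand-treated patients yields an off-target result.

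Its size is unknown. The figures of 1.0 and 0.5 grades, and the power values, rest on assumed effects, shares and stream sizes and on no change in untreated hands. It is tempting to say that results are simply diluted towards no effect, but the documents do not support that. It requires both a mix of sites and unchanged untreated hands, and the expected toxin redistribution and the allowance for further procedures leave the second condition open. Because these are secondary outcomes, the change is worth making but does not threaten the primary objectives.

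**What to change.** - Record the treated muscles and region (shoulder, elbow, wrist/finger/thumb) for every procedure, including later ones.
- For Keenan, House thumb and grip, prespecify the main analysis in patients, in any stream, whose procedure treated a wrist, finger or thumb muscle. Report the remaining patients separately and descriptively. Fix this rule before the data are examined, so that the set is not chosen by its results.
- Flag any patient who later has a hand procedure, so that the resulting change is not reported as off-target. Show the botulinum toxin units, which Beginning of Study already says will be tracked, beside these results.
- State which direction of grip change counts as benefit; Secondary Objective item 6 does not say.
- Reconcile triage item 2, which allows a median nerve procedure for the hand, with Design Details, which says that finger and wrist motor fibres cannot be isolated for ablation. The analysis set depends on what the percutaneous streams may treat.
- Optionally, give the number of patients at zero at both baseline and follow-up for Box and Block and the House Functional Scale.

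The cost is one added data field and a changed analysis set, with no new visit or measurement. The downside is smaller denominators for three secondary outcomes, so these results are best given as estimates with confidence intervals.

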Patients involved in this study have lived and managed their spasticity from years to decades. This clinic evolved after the sense of hopelessness that no more could be done with the traditional botulinum toxin centred plan. This multi-pronged treatment options offers the patient the choice and option to choose the treatment option they wish to undergo based on consultation with clinicians. The DNB clinic which occurs weekly is the only such clinic in Canada. The DNB is one of the rare instances where we can demonstrate what an intervention could look like. This study is not a clinical trial; thus, no patient is “enrolled” at random in a study arm. In fact, each patient is part of the decision-making tree. Patients and families may choose to forego surgery if it is the “best” option and undergo a cryo or radiofrequency neurotomy if they prefer to not undergo anesthesia, or surgical care. Patients may choose to have no change to their care pathway. Patients that do not participate in the study will undergo the same care as those that do not. All patients have the option of trying each of the options as a step wise approach to management is a typical surgical rehabilitation strategy. This study is an assessment of change from the selected clinical interventions. Finally, the patients will be enrolled after the decision to treat with a specific intervention has been selected.

Primary Objectives:

1-Degree of changes in spasticity as assessed by Modified Ashworth Scale³² from baseline and in 1, 3, 6, 9 and 12 months after the intervention. The test will be done by the trained assistant which is not enrolled in providing medical care. It will be graded as 0 (no spasticity), 1, 1+, 2, 3 and 4 which the affect part is rigid in flexion or extension.

2-Degree of changes in range of motion of tested joints as assessed by Tardieu Scale³² from base line and in 1, 3, 6, 9 and 12 months. The maximum of passive range of motion in slow movement(V1) and degree of catch in speed (V3) and active range of motion will be measured by goniometer.

3- Upper limb function changes as assessed by DASH³⁷ questionnaire (2006). It is a self-administered questionnaire that participants will be asked to fill out at baseline and in 1, 3, 6, 9 and 12 months. Final score will be calculated based on the provided formula and will be between (0), which means patient has no difficulty at all and (100) which means the worst outcome.

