To confirm that improvements in outcomes are statistically significant a paired t-test on the difference of proportions, applicable to pre-treatment and post-treatment, will be performed. Pearson's correlation and logistic regression will also be used to determine whether any key predictors are associated with any of the outcomes at final visit. We will employ repeated measures or linear mixed (multilevel) models of change to analyze within-person trajectories in all key outcomes for the intensive repeated measures data spanning the 12-month study period. Such models derive individual parameter estimates for baseline function and change pursuant to nerve or surgical procedure, and will directly index the magnitude in improvement for each outcome (pursuant to treatment) with each individual serving as their own control (i.e., with change indexed relative to each individual's own personal baseline).

If normal distribution in the outcomes does not stand, McNemar's test and Spearman correlation will be calculated instead of paired t-test and Person's correlation, respectively.

We will rely on Island Health Statistic for this process, the data will not leave Island Health and will be analyzed through REDCap. (Statistics provided by [name], Island Health)

Inclusion Criteria:

- Adult patient \geq 18 years old, with upper extremity spasticity causing functional impairment.
- Patients that have plateaued in outcomes in which the clinical examination suggests further interventions can be trialled.
- The clinical examination, including a V1 (maximal passive stretch) and V3 (Fast catch) on upper extremity examination that demonstrates further passive or active range may be possible, versus if contracture must be managed. For example, a fistled hand that can be forced open. This includes factors such as fluctuating tone or clonus interfering with assessment.
- The patient undergoes a diagnostic nerve block to determine if there is a reducible spasticity in the muscle versus contracture.
- The patient has been offered a neuroablative procedure or surgery and has elected to undergo the procedure. The patient has consented to undergo said procedure.

Exclusion Criteria:

[figure not shown]
- Patients where no consent or Assent is obtained
- Unable attend treatment schedule

Efficacy Evaluation/Schedule/length of the study:

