Patients will be recruited over a one-year period. All patients would have already been screened and elected to undergo one of the procedures with consent to procedure. All patients will require baseline measurements prior to their procedure. Efficacy will be measured by their assessments after the procedure using our outcome measures, including a twelve months follow up for the initial study but will remain for up to 24 months.

Visual Timeline:

Clinical Care and Research Activity Timelines

*Note, you may have more than one type of procedure, based on your response/recovery. You and your doctor would discuss this as it is a clinical decision. (standard clinical care)

Time required to complete study (months):

24 months.

Access to Patient Charts:

As part of our usual standard of care. The charts will be accessed by the treating physicians. The research assistant will require chart access to plot demographics and contact patients.

Incidental Findings:

Incidental findings are not expected in the ablation procedures as this is percutaneous and the ultrasound of the limb would have been done on two previous occasions. While not expected in upper

extremity surgery, surgical incidental findings include, abnormal anatomy, tumours. Any incidental finding would be reviewed with the patients and investigated fully by the research team and or their primary care givers, with appropriate referrals and imaging found.

Stopping rules:

[figure not shown]
The study would be stopped by the clinical team in the advent of treatment failure, or adverse events in conjunction with the CEC. It would be stopped if the REB or Health Authority stops the trial over research concern. Loss of funding is an unlikely cause of stopping as the treatments are funded, it is only the data collection salary that provides the largest expenditure.

References:

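### Do the 12-, 18- and 24-month figures around N = 50 conflict in a way that would cost 12-month visits?

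*Combined protocol and SAP*

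**What the plan says.** Three places in the combined protocol and SAP bear on the calendar.

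- **Sample Size Justification. Statistical Analysis.** N = 50 is a convenience sample for a pilot, with no power calculation. Past volume is given as more than 100 patients triaged over 18 months, and from this the plan projects: "it is anticipated that 50 target patients to be fully completed treatment in 18 months". The next sentence gives the working rate: "At 4-6 (divided between surgical and interventional) patients per month for 12 months, this is achievable based on this clinical experience".
- **Efficacy Evaluation/Schedule/length of the study.** "Patients will be recruited over a one-year period". Follow-up is twelve months for the initial study, with patients staying for as long as 24 months. The entry for time to complete the study is 24 months.
- **Primary Objectives.** For spasticity, assessments are set "from baseline and in 1, 3, 6, 9 and 12 months after the intervention", so the clock starts at the procedure and not at enrolment.

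Enrolment comes before the procedure. Under Beginning of Study: "After surgical or percutaneous neuroablative procedures are selected patients will be invited to enroll in the study". Under Pulsed radiofrequency Stream, waits are acknowledged but given no length: "To date our availability of time on the cryoneurotomy equipment is limited, and pulsed radiofrequency will allow for shorter waits".

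**The concern.** If treatment runs to month 18 and each patient is followed for 12 months from the procedure, the last visit is at month 30, while the stated total is 24. Even 12 + 12 = 24 leaves no slack, because it needs every clock-starting procedure done by month 12, and the plan sets no such limit. Patients join once a procedure has been chosen and may then wait for it.

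If data collection closed at month 24, patients treated late would lose the 12-month visit. That visit ends the trajectory for the mixed models, which cover "intensive repeated measures data spanning the 12-month study period". It also supplies the data for the correlation and logistic regression analyses of "whether any key predictors are associated with any of the outcomes at final visit". The loss would depend on treatment date, so it could fall more heavily on a stream with longer waits, and the streams are to be analysed individually. The mixed models can use incomplete trajectories, so the final-visit analyses would suffer most.

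**Working it through.** **Inputs.** N = 50; past triage above 100 in 18 months; rate *r* = 4 to 6 per month for 12 months; treatment projected complete in 18 months (all from the sample size section). Recruitment 12 months, follow-up 12 months, total 24 months (schedule section). Visits counted from the intervention (Primary Objectives).

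**1. Reproduce N = 50.** Patients in a year = *r* × 12.
- 4 × 12 = 48; 5 × 12 = 60; 6 × 12 = 72.
- Exactly 50 needs 50/12 = 4.17 per month, inside 4 to 6.

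The sample size is reachable on the plan's own rate.

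**2. Check the schedule section alone.** 12 + 12 = 24. Recruitment, follow-up and total duration agree.

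**3. Last 12-month visit at the stated rate, with no wait before the procedure.** Month = 50/*r* + 12; slack against month 24 = 12 − 50/*r*.

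| *r* per month | Months to treat 50 | Last 12-month visit | Slack (months) |
|---|---|---|---|
| 4 | 12.5 | 24.5 | −0.5 |
| 5 | 10.0 | 22.0 | 2.0 |
| 6 | 8.3 | 20.3 | 3.7 |

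At 4 per month, 48 patients are treated by month 12. The other two are treated by month 12.5, so their last visits fall at most two weeks after month 24. At 5 or 6 per month there is room for a wait of about 2 to 3.7 months.

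**4. The literal 18-month reading.** Suppose 50 patients are treated evenly from month 0 to month *L*. The share treated after month 12 is (*L* − 12)/*L*.
- *L* = 12: 0 patients; last visit at month 24.
- *L* = 15: 3/15 × 50 = 10 patients; last visit at month 27.
- *L* = 18: 6/18 × 50 = 16.7, about 17 patients; last visit at month 30. Of these, 3/18 × 50 = 8.3, about 8, would also have the 9-month visit after month 24. The latest 6-month visit is at 18 + 6 = 24.

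The *L* = 18 case implies 50/18 = 2.8 per month, below the stated 4 to 6. The plan gives no treatment dates, so the even spread is an assumption.

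**5. Other readings of the two loose figures.**
- If the 18 months includes follow-up, all 50 must be treated by month 6, or 50/6 = 8.3 per month. That exceeds 4 to 6, so this reading fails.
- If the 18 months covers staged or repeat procedures, the figures can fit. The plan lets a patient have more than one type of procedure, so first procedures could be done by about month 12 and later ones by month 18. This holds if follow-up runs from the first procedure, which the text does not specify.
- If 24 months is the stay per patient, no visit is cut off. The calendar is then 12 + 24 = 36 to 18 + 24 = 42 months.

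**6. Is there a cut-off?** The text has no rule that closes data collection at month 24 with visits outstanding. The 24 months is an entry for time required. Assessments take place on the days of routine clinic follow-up.

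**The case for a change.** The strongest case for a change is that 18 + 12 = 30 is correct and the text never reconciles it with 24. Recruitment is not treatment: patients may take the study package home, get a reminder two weeks later, and may wait for equipment. The two rates also differ, at 2.8 against 4 to 6 per month. Past triage of about 100/18 = 5.6 per month means that 4.17 per month needs up to 4.17/5.56 = 75% of those triaged. The 18-month sentence implies about half (50 of 100), and patients whose toxin dose is altered are not studied. On that slower rate, one recruitment year yields 2.78 × 12 = 33 patients, not 50.

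Part of this stands. The 18-month phrase does not fit the sentence after it, the 24-month total has little slack at the low end of the rate, and the text does not say whether the longer stay is per patient or for the whole study. The timeline graphic is not in the text available and could bear on this.

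The inferred damage does not stand. The 18 months follows directly from the look-back period for triage and reads as that window carried forward. It is not given as a last procedure date or an enrolment limit. The wait has no stated length, and the sentence that mentions it says pulsed radiofrequency will shorten it. As no power claim is attached to N = 50, a somewhat smaller pilot would contradict no calculation.

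**Conclusion.** The mismatch is real but amounts to a loosely worded feasibility sentence, and no change to the plan is needed. The operative schedule is consistent, and N = 50 lies within the 48 to 72 that the stated rate gives. At that rate, with no wait before the procedure, the worst case is about two patients passing month 24 by up to two weeks. A wait could push more visits past month 24, but the documents give no length for it.

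The figure of about 17 of 50 depends on two assumptions together: treatment spread evenly to month 18, and collection stopping at month 24 whatever is outstanding. The first implies a rate below the plan's own, and no passage states the second. Because the schedule ties visits to the intervention, a team following it would see each patient to 12 months after the procedure and close the study when the last visit is done. The cost would be some extra assessor time, up to about 30 − 24 = 6 months in the extreme case. Clearer wording of the two figures would alter no estimate, analysis or conclusion of this exploratory pilot. The judgement would be different if the study were funded or approved with a fixed stop at month 24, which the text does not say.
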